## Flu2Text: A Multi-Site Study assessing an Intervention for 2nd Dose of Influenza Vaccine

### Overview of the study

This study will assess the impact of text message reminders on the receipt of the second dose of influenza vaccine and will take place in 40-50 practices over two influenza seasons.

This study includes a sample of up to 4,000 parents over the course of two flu seasons (up to approximately 40-250 parents any of 40-50 sites per influenza season). Eligible parents will have a child who received their first vaccine dose and are in need of 2 doses that season. The study will include parents who have a 6-month through 8-year-old child (or a child who is of the age that necessitates 2 doses, should age recommendations change as determined by the CDC) who received their first vaccine dose and is in need of 2 doses that season. Current recommendations require 2 doses for certain children 6 months through 8 years old.

Within each practice site, parents will be randomized to receive either:

- 1) a series of text message reminders embedded with influenza vaccine health-literacy promoting information, or
- 2) usual care

- *Season 1 (2017-2018):* usual care alone
- *Season 2 (2018-2019):* usual care plus a text message containing a link to health and parenting information from the American Academy of Pediatrics website

The primary outcome will be receipt of two doses of influenza vaccine by the end of the season (April 30). A secondary outcome will be timeliness of receipt of 2nd dose.

The study will be conducted over the 1st season (September 2017–April 2018) as an effectiveness trial and the 2nd season (July 2018–April 2019) as a replication study to validate the approach and allow refinement based on parent and practice feedback. The intervention targets the parent-child dyad.

### Background

Influenza, as evidenced by seasonal epidemics, remains a significant and largely preventable source of morbidity and mortality resulting in an estimated 31 million outpatient visits, 226,000 hospitalizations, and 3,000 to 49,000 deaths annually (depending on the virulence of the circulating strain), along with a high cost burden from direct medical expenses and days lost from work. Young children, the focus of this proposal, are at especially high risk for hospitalization and serious influenza complications including pneumonia and neurological outcomes like seizures and encephalopathy. They are also a source of transmission to other high-risk household members. However, influenza vaccine coverage is low. Only 58.9% of U.S. children 6 months to 17 years-old receive at least one needed influenza dose annually. Young children <9 years are at particular risk for under vaccination because they require 2 doses at least 4 weeks apart in the first influenza season they are vaccinated, since one dose does not confer adequate influenza protection; some previously vaccinated children also require 2 doses in subsequent seasons depending on their previous influenza vaccinations. Even among those who need two doses in a given season and who receive the first dose, only 40-60% receive the second dose.

Timeliness is also key, as children are not fully protected until two weeks after receiving the second dose, many children do not receive this second dose close to 4 weeks after the first, as recommended. This delay leaves many children unprotected when influenza virus begins circulating. Increasing timely receipt of second doses is also a worthwhile focus as parents (meaning the adult in a parenting role, including guardians) have already “accepted” vaccination as evidenced by their child receiving the first dose.

### **Protocol**

This proposed study will assess the impact of personalized text message reminders embedded with influenza vaccine health-literacy-promoting information versus usual care on the outcome of receipt of the second dose of influenza vaccine in a given influenza season.

### **Study Aims:**

**AIM 1:** To compare the effectiveness in increasing receipt of the second dose of influenza vaccine of personalized text message reminders embedded with influenza vaccine health-literacy-promoting information versus usual care in a diverse pediatric population in need of two doses in a given influenza season.

**AIM 2:** To compare the effectiveness in improving the timeliness of the second dose of influenza vaccine of personalized text message reminders embedded with influenza vaccine health-literacy-promoting information versus usual care in a diverse pediatric population in need of two doses in a given influenza season.

**AIM 3:** To assess parental and child characteristics that modify text message effectiveness.

## **Study procedures**

### **Practice inclusion criteria:**

- Ability to recruit a minimum of 40 English or Spanish speaking parents per season
- Ability to check the office medical records and/or the city/state immunization information system of the child of the participating parent to confirm dates of first and second influenza vaccination and related visit dates in each season (and ability to provide these dates to the study team)

### **Practice exclusion criteria:**

- Practices that already use or plan to use text message reminders for the second dose of influenza vaccine during the study period

### **Parent inclusion criteria:**

- Parenting adult (or legal guardian) of a child that:
  - is between 6 months through 8 years at the time of enrollment (or a child who is of the age that necessitates 2 doses, should age recommendations change as determined by the CDC)
  - received 1st dose of influenza vaccine within last 7 days (6 days plus date of vaccination)
  - receives care at study site
  - needs 2 doses of influenza vaccine that season as determined by their provider at the study site.
- Ability to communicate in English or Spanish
- Has a cell phone that has text message capabilities

### **Parent exclusion criteria:**

- Parenting adult of a child that:
  - already enrolled in the study in this or the previous season (see Attachments E.2 & I.2)
- Unable to communicate in English or Spanish
- Unable to receive or read text messages on their cell phone

Below we outline the different procedures planned for the study:

**Season One:** When parents/children come to the practice to receive an influenza vaccine, a member of the care team at the practice site will use the Eligibility Flow Sheet to determine their eligibility for the study. If eligible and parent is interested, the care team member will introduce the study to the parent by providing a parent study information card and a copy of the parent information sheet, available in either English or Spanish. Parents who are potentially interested in the study will be asked to send a text message to the study text message platform. Families will be called to be enrolled. Parental verbal consent and HIPAA authorization will be obtained via phone by study staff.

**Season Two:** Parents presenting for visits with age-eligible children up to/including the initial flu vaccination visit will receive a study information sheet in either English or Spanish. Providers and practice staff will be asked to approach all eligible parents and provide them with the information sheet. At the visit when the child will receive the first flu shot, a provider or member of practice staff will use the Eligibility Flow Sheet to determine whether the child needs two flu shots this season and whether the child's parent can communicate in either English or Spanish. This recruiting practice staff member will present the Parent Information Sheet to the parent. If the parent is interested and the practice enrolled patients in the 2017-18 flu season, the recruiting practice staff member will assess whether the parent already participated in the study. If there is more than one eligible child in the family, the recruiting practice staff member will enroll the child whose birthday comes next in the calendar year. For example,

---

if today is October 1 and one child's birthday is January 21 and the next child's birthday is March 4 (regardless of year) then the child with the January 21 birthday should be selected. If the parent is eligible and wishes to participate, verbal consent and HIPAA authorization will be obtained by an HST-certified provider or practice staff member (recruiting practice staff member) at the study practice sites.

### **Parent randomization**

Randomization will occur with a 1:1 allocation ratio stratified by:

- clinical site (such that each site will have a balance of intervention and usual care plus participants)
- child's age group (6-23 months vs. 2-8 years)
- parental language (English versus Spanish preference)

To ensure allocation concealment (a technique used to prevent selection bias), the CHOP/Penn statistician will prepare for each site a separate randomization list stratified by age and language, using randomly permuted blocks with varying block sizes.

If the parent is assigned to usual care, they will receive the existing influenza vaccination protocol for any given practice. This may include other forms of influenza vaccine reminders. In season 2, caregivers randomized to usual care will be sent a message upon enrollment containing a link to health and parenting information from the American Academy of Pediatrics website. If a parent is assigned to the intervention arm, we will follow the protocol under *Study Intervention: Text Messages*.

#### ***Study Intervention: Text Messages***

Messages will be sent in English or Spanish based on parent preference.

Using date of initial vaccine as day 0, text messages will be sent to all parents randomized to the intervention on the following days:

- Day 14: notifying parents that their child is in need of a second flu shot.
- Day 21: educational text messages, with interactivity, through which parents can select to receive more information via text message.
- Day 25: letting parents know when and where they will need to go to receive the second shot
- Day 28 (day vaccine is due): it is now time to take [child] to be vaccinated (2nd flu shot).
- Day 42 (2 weeks after it is due): another interactive message will assess potential vaccine barriers and offer selected responses.

Texts will stop after day 42. We will not be able to know from the practices in time to stop messages after a child was vaccinated. However, as the shot is not due until day 28, it would likely only be the day 42 message that could come after the child was vaccinated. That message has been worded to first assess whether the child received the vaccine.

**Dates of influenza vaccinations and related visit dates:** Dates of influenza vaccinations and related visit dates will be collected from the practices. The part of the Patient Enrollment/Outcomes Forms that stays with the site will have child's first and last name and date of birth. The site will use this to identify the medical record, extract relevant influenza vaccination dates and related visit dates and transfer this information to the research team. Practices will do this by using their medical records and/or by checking their city or state immunization registry should the practice have no record of receipt of subsequent influenza doses for the current season.

## **Statistical Analysis Plan (SAP) – Flu2Text - v1.6**

### **Date of final SAP: September 12, 2019**

This plan, based on the original proposal and the IRB protocol, will guide analyses. It follows the aims outlined in the proposal. In keeping with recent guidance of the American Statistical Association, we will avoid statements about “statistical significance”. When reported, p-values will be continuous, unless they are below 0.001, when we shall use the notation “ $p<0.001$ ”, in keeping with general guidance on very small p-values. We shall report p-values with 2 decimal places if they are larger than 0.10 and to 3 decimal places otherwise. Point estimates and confidence bounds will be the primary means of reporting results and their precision. Primary analyses are reported below where indicated. Software tools are also listed, but are subject to modification if they fail to converge or produce results.

For overall guidance, we will follow those from [New England Journal of Medicine](#) (Last accessed, Sep 11, 2019).

We shall date this SAP upon agreement and completion and then date all amendments.

## 1.0 Data management

We shall examine each covariate to identify ambiguities and to categorize when appropriate to avoid zero and small categories. All refinement of covariates will occur prior to any examination of outcomes.

Cross classifying X's will determine which X's are correlated, aliased, how many levels can be collapsed. The goal will be to find a set of covariates for use in describing the sample and comparing the two treatment groups for balance. In these analyses, we should not be looking at outcome.

## 2.0 Analysis (A) Primary analysis: As randomized (Aims 1 and 2).

**AIM 1:** To compare the effectiveness in increasing receipt of the second dose of influenza vaccine of personalized text message reminders with embedded influenza vaccine health-literacy-promoting information versus usual care in a diverse pediatric population in need of two doses in a given influenza season.

**AIM 2:** To compare the effectiveness in improving the timeliness of the second dose of influenza vaccine of personalized text message reminders with embedded influenza vaccine health-literacy-promoting information versus usual care in a diverse pediatric population in need of two doses in a given influenza season.

### 2.0.1 Analyses will proceed separately by season

Seasons 1 and 2 will be analyzed separately.

Secondary analysis will combine seasons, adjusting for season as a stratifying factor. Site will be considered to be a separate stratum by season.

## 2.1 Analysis – binary outcomes – primary analysis and outcome

Outcome = Receipt of the second dose of influenza vaccine, a binary outcome.

By April 30, the end of the season - primary

By Day 42 from the day of first dose - secondary

Formal question to be answered: "If a group of children were alternatively assigned to the two treatment arms, what would be differences in completion of influenza vaccines by the end of the season, defined as April 30th of each season?"

The alternative and secondary endpoint will evaluate receipt of the second dose as of day 42 from the date of the child's first dose.

Randomization, if successful, should lead to exchangeability of two groups and permits estimation of the treatment differences (as the control group should be the same as the intervention group).

Preliminary analysis of time from the first dose to time of randomization showed no difference between intervention and control groups, and reflects successful randomization. This analysis was conducted as part of assessing balance and without regard to outcomes.

Primary analyses will proceed where possible with assumption-free methods. Dropout was negligible and so adjustment for dropout was not needed nor specified in the final SAP.

### **2.1.1 Testing for balance from randomization based on patient-level covariates**

The initial check will be whether randomization produced balance of the sites and covariates. For this check, we will fit a model:

Outcome is treatment assignment. Logistic regression – with all covariates included.

1. Check that overall likelihood ratio statistic is not significant.
2. Suggests overall balance consistent with successful randomization.

Balance check covariates:

- time from 1st (initial) dose to randomization
- child age
- child gender
- text language
- child health insurance

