### 2.1.3 Analysis with covariates (if check on balance fails)

#### 2.1.3.1 Conditional logit models (likely not applicable owing to randomization)

Conditional logistic regression model, adjusted for covariates, stratified by site.

Stata: clogit outcome treatment covariates, group(site)

Compare with the model (covariate unadjusted) such as Mantel Haenszel approaches.

Stata: clogit outcome treatment, group(site)

Do the estimates of the effect of treatment differ between these two models? If yes, then some chance imbalance in covariates across treatment groups is imparting some bias in the unadjusted estimates.

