### 2.3.5 Restricted mean survival curves (RMST)

RMST will not be a primary analysis, and we will not consider it to be a separate look at the data. Rather, it is another method of reporting the data, and we will not adjust confidence bounds for multiple comparisons.

We will implement restricted mean survival time analysis to compare intervention versus usual care groups (if needed, after adjusting for covariates that are not balanced

between groups) and to arrive at meaningful estimates that do not require proportional hazards assumptions.

We have moved beyond hazard ratios because of the assumptions underlying Cox models and the shortcoming of interpretations (Hernan 2010). If we set a truncation time (Day 42), then RMST has the interpretation "if we follow children for 42 days, they will receive the second vaccine on average by day X" (Royston 2011, 2013). Estimation of between group differences are also possible. The more theoretical interpretation is the area under the survivor function until the time of truncation.

Preiminary analysis of available time per child (analysis blinded to outcome and to the treatment assignment) showed that between 84% and 90% (depending on season) of children has observation windows that extended to day 90 from date of first dose.

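### Covariate adjustment of the binary outcomes depends on failing an omnibus balance test, which is a poor trigger and is undersized under this stratified randomisation

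*Combined protocol and SAP*

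**What the plan says.** SAP 2.1.1 introduces the check with "The initial check will be whether randomization produced balance of the sites and covariates". The model has treatment assignment as its outcome and is described as "Logistic regression – with all covariates included". Five covariates are listed: delay from first dose to randomisation, age, gender, text language and insurance. Site is not on the list. One instruction decides the result: "Check that overall likelihood ratio statistic is not significant". No significance level is given.

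Section 2.1.3 is headed "Analysis with covariates (if check on balance fails", and its only subsection is "Conditional logit models (likely not applicable owing to randomization". It does not name the covariates to be adjusted for.

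The protocol's Parent randomization section says "Randomization will occur with a 1:1 allocation ratio stratified by" and lists clinical site, child's age group and "parental language (English versus Spanish preference", with permuted blocks of varying size.

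The Mantel-Haenszel relative risk (2.1.2.1) and risk difference (2.1.2.2) use strata formed from site and language. Age group, the third randomisation factor, is absent. For restricted mean survival time (RMST), 2.3.5 has its own wording: "if needed, after adjusting for covariates that are not balanced".

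**The concern.** There are two faults, and the first is the larger.

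1. **The gate.** When allocation is random, any difference in baseline covariates is due to chance, so a significant result is a false alarm about the randomisation. Adjustment is worth doing when a covariate predicts the outcome, and the test carries no information on that. A non-significant result is no reason to leave a prognostic covariate out.

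2. **Its size.** Stratified blocks hold language and age group close to balance. Those terms still use degrees of freedom but add almost nothing to the likelihood-ratio statistic, so the usual chi-square reference is too demanding.

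At stake is whether baseline data already in hand, and one of the trial's own randomisation strata, ever enter the analysis of the primary outcome. As written, they almost never would.

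**Working it through.** The documents give no level, power or size for the balance check, so there is no stated figure to reproduce.

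**Inputs from the documents**
- Five covariates in the check (SAP 2.1.1).
- Site, age group and language as randomisation strata (Parent randomization).
- Up to 4,000 parents over two seasons, so up to 4,000 / 2 = 2,000 per season (Overview).
- Second-dose completion of 40-60% (Background); 50% is used.

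**Assumptions**
- Level 5% for the check.
- Blocks of 2, 4 and 6.
- Insurance split 50/50.
- Prognostic gap of 10 to 20 points in completion between insurance groups.

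**Step 1: how often the gate opens.** The 5% critical value of chi-square on 5 df is 11.07. If age and language contribute about zero, the statistic behaves like chi-square on 3 df:

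P(chi2_3 > 11.07) = 1.1%.

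At a nominal 10% the rate is 2.6%, and at 20% it is 6.3%. The SAP lists age without saying it is grouped. If age were not constrained at all, the nominal 5% test would give P(chi2_4 > 11.07) = 2.6%.

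**Step 2: simulation.** Stratified permuted blocks within site, age group and language; 50 or 25 sites with 40 children each; 1,200 runs per scenario; nominal 5%:

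| Allocation and age coding | Rejection rate |
|---|---|
| Simple randomisation | 4.3-6.0% |
| Stratified blocks, age in two groups | 0.8-1.0% |
| Stratified blocks, continuous age | 1.1-1.7% |

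The test has about the right size under simple randomisation and loses it under the trial's own scheme.

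**Step 3: what the gate misses.** The three covariates that blocking leaves free are insurance, gender and delay to randomisation. If they are independent, the chance that at least one has an individual p < 0.05 is 1 - 0.95^3 = 14.3%. Among those trials:
- the planned 5-df test is silent in 92%;
- a correctly sized 3-df test is silent in 66%.

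Correcting the degrees of freedom therefore does not rescue the gate. With everything else perfectly balanced, one covariate would need |z| = sqrt(11.07) = 3.33 to trip the test. At n = 2,000 that is 3.33 x sqrt(4 x 0.25 / 2,000) = 7.4 points of imbalance.

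**Step 4: effect on the risk difference.** Shift = imbalance x prognostic gap. Imbalance at |z| = 1.96 is 1.96 x sqrt(4 x 0.25 / n). SE of the risk difference is sqrt(4 x 0.5 x 0.5 / n).

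| n per season | Imbalance (points) | Shift, 10-20 point gap (points) | SE (points) | Shift / SE |
|---|---|---|---|---|
| 2,000 | 4.4 | 0.4-0.9 | 2.2 | 0.2-0.4 |
| 1,000 | 6.2 | 0.6-1.2 | 3.2 | 0.2-0.4 |

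**Step 5: precision.** With a 50/50 split and 50% completion, the share of outcome variance explained is gap^2 x 0.25 / 0.25, which is 1% to 4%. The SE would fall by 1 - sqrt(0.99) = 0.5% to 1 - sqrt(0.96) = 2%, before allowing for overlap with the site and language strata.

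**The case against.** The strongest reply is that little is lost. The comparison is randomised. The relative risk and risk difference already stratify by site and language, and SAP 2.1 reports no difference between arms in the delay to randomisation. A gate that hardly ever opens amounts in practice to a fixed stratified analysis, with little data-driven model switching. The check also has a legitimate use: a faulty allocation list could show up in the strata. All of this stands, and it limits the weight of the point. It does not make the test a sound trigger, and it does not explain why age group is left out of the strata.

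A reader might infer more than the documents support:

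- *That only unadjusted results will be reported.* Site and language are in the primary estimates. The confirmatory randomisation-based syntax in 2.3.3 lists adjustment variables without any gate, and 2.3.5.1 names a command for covariate adjustment.
- *That the same omnibus test governs RMST.* Section 2.3.5 speaks of individual covariates that are unbalanced and names no test. It is balance-triggered, but not by this check.
- *That the test can never fire.* That follows only if site indicators are in the model. The introductory sentence mentions sites, but the section title refers to patient-level covariates and the list of five omits site. No result here relies on that version.
- *That imbalance would be hidden.* Section 1.0 plans a comparison of the arms for balance, so an insurance difference could be seen there. What is missing is a planned response to it.

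**Conclusion.** The point holds for the binary outcomes at April 30 and Day 42. Making adjustment conditional on the omnibus test is the main fault. Including factors that randomisation already balances makes it worse, cutting a nominal 5% test to about 1% (1.1-1.7% in simulation with continuous age). The covariates left exposed are age group, insurance and gender.

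The consequence is modest. A reader might conclude that the primary estimate is biased or invalid. It is neither: over repeated randomisation it is valid, and the shift arises only conditionally on a chance imbalance. For one covariate at |z| = 1.96, a 5% event, the shift is 0.2 to 0.4 SE. The loss of precision is small.

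The sizes rest on an assumed 5% level, block sizes, 50% insurance prevalence, 1,000 to 2,000 children per season and a prognostic gap, none of which the documents state; they give only the 4,000 ceiling over two seasons. The argument against the gate needs none of these. The change is worth making because it is cheap, not because the trial's conclusion is in danger.

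**What to change.** - In 2.1.1, keep the balance table, and the model if wanted, as description or as a check that allocation was carried out correctly. Remove it as the trigger for 2.1.3.
- For both binary outcomes, do one of the following whatever the balance shows. Either add age group to the site-by-language strata of the Mantel-Haenszel estimates, or pre-specify a supportive adjusted risk difference and relative risk, reported beside them, using regression standardisation with site, age group, language, insurance and gender.
- In 2.3.5, replace the conditional adjustment with the same fixed covariate set.
- Record the change as a dated amendment in section 5.0.

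Cost: SAP wording and, under the second option, one more estimate per outcome with some dependence on a model. That sits less well with the SAP's preference for assumption-free methods, which is why it should be supportive. Adding age group to the strata keeps the planned method, but gives up to four cells per site, about 10 children each at 40 per site; cells with only one arm contribute nothing.
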